6.3.2. Sensitivity Analysis of Primary Endpoint

The following sensitivity analyses of the primary endpoint will be performed:

- Using composite estimand
- Using hypothetical estimand

6.4. Secondary Efficacy Endpoints

6.4.1. Definition of Secondary Efficacy Endpoints

Secondary efficacy endpoints include:

- Change from baseline in ESSDAI total score at Week 12
- Change from baseline in ESSPRI total score at Week 12
- Change from baseline in ESSDAI total score at Week 24
- Change from baseline in ESSPRI total score at Week 24

6.4.2. Analysis Methods for Secondary Efficacy Endpoints

Each secondary endpoint will be analyzed using a mixed-effect repeated measures (MMRM) model with treatment, randomization stratification factors, visit, treatment-by-visit interaction as fixed effects, subjects as a random effect, and the respective baseline value (ESSDAI or ESSPRI) as a covariate. The Kenward-Roger method will be used to estimate the degrees of freedom. Each of the four endpoints will be tested separately at the 2-sided 0.05 level. The unstructured (UN) variance-covariance matrix of repeated measures will be considered first. If a model does not converge, then ARH(1) structure will be applied.

For each secondary endpoint, adjusted means (LS means) and 95% confidence intervals (CIs) obtained from the model will be presented for Weeks 12 and Week 24 time points.

Missing data will be handled using the method described in [Table 3](#).

The inferential analyses of the secondary endpoints will be based on the treatment policy estimand (main analysis of each secondary endpoint). Sensitivity non-parametric analyses of the secondary endpoints will be performed on rank-transformed data utilizing ANCOVA models with treatment group and stratification factors as effects and the rank-transformed baseline value as a covariate.

In addition, secondary efficacy analyses will be repeated for the hypothetical estimand and composite estimand.

Descriptive statistics (n, mean, SD, median, Q1, Q3, minimum, and maximum) will be presented by visit and treatment group, overall and for the subgroups listed in [section 3.4](#).

Line plots for median (Q1, Q3) change from baseline, mean (+/- 95% CI) change from baseline, and adjusted mean (LS mean) change from baseline (+/- 95% CI) will be provided for ESSDAI total score, ESSPRI total score and its components.

In addition, the box plots for ESSDAI total score and ESSPRI total score and change from baseline will be presented by visit and treatment group.

A cumulative plot of change from baseline in ESSDAI total score and in ESSPRI total score at Week 12 and Week 24 will be presented by treatment group.

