1.2. Study Design

This is a Phase 2, multicenter, randomized, double-blind, placebo-controlled study to evaluate the safety and efficacy of filgotinib, lanraplenib (GS-9876), and tirabrutinib (GS-4059) in adult male and female subjects with active SjS.

At Day 1, eligible subjects will be randomized 1:1:1:1 to daily oral filgotinib (200 mg), lanraplenib (30 mg), tirabrutinib (40 mg) or placebo to match (PTM). Randomization will be stratified by: use of concurrent immunomodulatory drugs at baseline (Y/N: conventional synthetic disease modifying antirheumatic drugs (csDMARD[s]) or corticosteroids), and the hematologic + biological component scores of the EULAR Sjogren's syndrome disease activity index (ESSDAI) obtained at screening (combined score of <2 or ≥ 2).

[figure not shown]
Stable medications at Day 1 should be continued during the study dosing period through Week 48. Dose adjustments for toxicities and dose adjustment of corticosteroids are allowed after Week 12. Subjects will return to the study site for scheduled study visits at Weeks 2, 4, 8, 12, 18, 24, 26, 28, 32, 36, 42, and 48 ([Appendix 1](#)).

At completion of the Week 24 visits, subjects on placebo will be re-randomized 1:1:1, in a blinded fashion, to daily oral filgotinib (200 mg), lanraplenib (30 mg), or tirabrutinib (40 mg) without further stratification. Dosing and assessments for all subjects will continue through Week 48.

CCI

Subjects who discontinue study drug for any reason (other than noncompliance) may continue to participate in scheduled study visits and procedures, as long as deemed medically appropriate by the investigator. Subjects who discontinue all study participation will have an early termination (ET) visit; these subjects, and those who complete the study, should return to the study site for a follow-up visit, 4 weeks after the last dose of study drug (subjects who have discontinued study drug \geq 4 weeks prior to the ET/Week 48 visit, do not need a follow up visit).

Figure 1. Study Design Schematic

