6. EFFICACY ANALYSES

Efficacy endpoints will be evaluated for the following treatment periods: placebo-controlled period up to Week 24 and the entire study up to Week 48.

The primary and secondary endpoints analyses will be based on the estimands presented in the [Table 3](#).

Table 3. Efficacy Estimands

Binary Endpoint	Treatment Policy (main)	Hypothetical	Composite
Population	FAS	FAS	FAS
Intercurrent Event	Ignore all intercurrent events	
 • Treatment discontinuation • Start of prohibited medication • The dose change of medication that is required to be stable Data after the event are treated as missing	
 • Treatment discontinuation • Start of prohibited medication • The dose change of medication that is required to be stable Data after the event are treated as no response
Main Estimator	Stratified CMH test with imputation of missing data using logistic regression	Stratified CMH test with imputation of missing data using logistic regression	Stratified CMH test with non-responder imputation of missing data

Continuous Endpoints	Treatment Policy (main)	Hypothetical	Composite
Intercurrent Event	Ignore all intercurrent events	
 • Treatment discontinuation • Start of prohibited medication • The dose change of medication that is required to be stable 	
 • Treatment discontinuation • Start of prohibited medication • The dose change of medication that is required to be stable
Main Estimator	The treatment difference will be estimated using a mixed effects model for repeated measures. Missing data will be imputed using multiple imputation	The treatment difference will be estimated using a mixed effects model for repeated measures. Missing data will be imputed using multiple imputation	The treatment difference will be estimated using a mixed effects model for repeated measures. Missing data will be imputed using multiple imputation based on observed data from the placebo group

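### The MMRM for the secondary endpoints combines a random subject effect with an unstructured covariance, so one parameter is redundant and the ARH(1) fallback could be triggered needlessly

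*SAP*

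**What the plan says.** SAP 6.4.2 covers the change in ESSDAI and ESSPRI at Weeks 12 and 24: "Each secondary endpoint will be analyzed using a mixed-effect repeated measures (MMRM) model". The model terms include "treatment-by-visit interaction as fixed effects, subjects as a random effect, and the respective baseline value". On covariance it says "The unstructured (UN) variance-covariance matrix of repeated measures will be considered first", and then "If a model does not converge, then ARH(1) structure will be applied". On inference it says "The Kenward-Roger method will be used to estimate the degrees of freedom" and "Each of the four endpoints will be tested separately at the 2-sided 0.05 level".

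Table 3 in SAP Section 6 adds, for the main estimand, "The treatment difference will be estimated using a mixed effects model for repeated measures. Missing data will be imputed using multiple imputation". SAP 6.1 sets the number of imputed data sets at 20, each analysed by the MMRM and pooled by Rubin's rule.

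Three things are not stated:
- whether the random subject effect is dropped when the matrix is unstructured;
- whether it stays in the model under ARH(1);
- what happens if only some of the 20 imputed data sets fail to converge.

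**The concern.** An unstructured matrix already holds a free variance for every visit and a free covariance for every pair of visits. A random subject intercept adds one constant to every element, and the matrix can absorb that constant without any change in fit. The data therefore cannot estimate the subject variance, and the information matrix of the covariance parameters, which Kenward-Roger uses, is singular.

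A singular information matrix is a recognised cause of non-convergence, and non-convergence is what moves the analysis to ARH(1). A redundant term could thus decide the covariance model behind the ESSDAI and ESSPRI tests. The model is also fitted many times: two scores, three estimands and 20 imputed data sets make 2 × 3 × 20 = 120 fits. Without a rule, pooling could mix unstructured and ARH(1) results.

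**Working it through.** **Inputs.** The SAP lists "scheduled study visits at Weeks 2, 4, 8, 12, 18, 24, 26, 28, 32, 36, 42, and 48". By the schedule in SAP Appendix 1, ESSDAI up to Week 24 is measured at Weeks 4, 8, 12, 18 and 24 (T = 5), and ESSPRI at Weeks 2, 4, 8, 12, 18 and 24 (T = 6). Stopping at Week 24 is an assumption. About 35 subjects per arm in four arms comes from SAP 1.3. The plan states no figure that could be reproduced here.

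**Step 1: count parameters.** The marginal covariance is V = s²·J + R, where J is a matrix of ones and R is unstructured. R has T(T+1)/2 parameters.
- ESSDAI: 5·6/2 = 15; with s², 16. Rank of the map to V: 15.
- ESSPRI: 6·7/2 = 21; with s², 22. Rank: 21.
- All visits to Week 48 (T = 10 and 12): 56 against rank 55, and 79 against rank 78.

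Exactly one parameter is redundant each time. Any V can be written with R = V − s²·J for every s² that keeps R positive definite.

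**Step 2: likelihood.** In one simulated data set (4 × 35 subjects, T = 5), s² = 0, 1.00, 2.00 and 3.60 all gave −2 REML log-likelihood 1731.536, Week 24 contrast 0.416 and SE 0.589. For an assumed covariance, the smallest eigenvalue of the information matrix is 0 to rounding with the random effect. Without it, the value is 10.7 (T = 5) and 8.4 (T = 6).

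**Step 3: ARH(1) alone.** It sets cov(j,k) = s_j·s_k·ρ^|j−k|, with j and k counting visits, so one ρ serves every gap. The gaps are 4, 4, 6, 6 weeks (ESSDAI) and 2, 4, 4, 6, 6 weeks (ESSPRI). Take as an assumed truth 0.4 + 0.6·g^weeks. With g = 0.90 the adjacent correlations are:
- 2 weeks: 0.4 + 0.6·0.90² = 0.886
- 4 weeks: 0.4 + 0.6·0.90⁴ = 0.794
- 6 weeks: 0.4 + 0.6·0.90⁶ = 0.719

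Minimising log|V| + tr(V⁻¹S), with S the assumed truth, gives the large-sample ARH(1) fit. Ratios of fitted to true values for g = 0.90 to 0.95, with SE ratio = √(variance ratio):

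| Score | Week 12 variance | Week 12 SE | Week 24 variance | Week 24 SE |
|---|---|---|---|---|
| ESSDAI | 1.00 | 1.00 | 1.075–1.080 | 1.04 |
| ESSPRI | 1.10–1.115 | 1.05–1.06 | 1.18–1.19 | 1.09 |

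A 9% overstated SE moves the critical value from 1.96 to 1.96 × 1.09 = 2.14. The true two-sided level becomes about 0.033, and a test with an assumed 80% power drops to about 75%.

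**Step 4: sensitivity to the assumption.**
- Compound symmetry (correlation 0.3, 0.5 or 0.7): every ratio is 1.00.
- Independent error added, 0.4 + (0.6 − e)·g^weeks with e on the diagonal, e = 0.2 or 0.3: Week 24 SE is overstated by 0.7–1.5% (ESSDAI) and 1.3–3.0% (ESSPRI).

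**Step 5: random intercept kept with ARH(1).** This model is identifiable (7 parameters, rank 7; 8, rank 8). For other assumed covariances (compound-symmetric, autoregressive and mixed correlations, SD rising 40% over visits), the SE ratio was 0.96–1.00 at Week 12 and 0.91–1.00 at Week 24. At worst, a nominal 0.05 becomes about 0.059 and 0.076. What the fallback does therefore depends on which version is meant.

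**The case against.** The phrase may be loose. The section names an MMRM and assigns the unstructured matrix to the repeated measures, so listing subjects as random may only identify the clustering unit. If so, the intended model is sound and one sentence needs correcting. That reading is plausible, but nothing else in the SAP confirms it, and a programmer following the text could code both terms.

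A reader might infer that the model is bound to fail. The check does not show that: it shows a flat likelihood, not a failed fit. Software may set the subject variance to zero, perhaps with a warning, and converge. Step 2 shows that the contrast and its model-based SE are then the same. Only the Kenward-Roger degrees of freedom remain open, since they depend on how the redundant parameter is handled.

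The loss also needs a chain of events: literal coding, a failed fit, a switch to ARH(1), and a true covariance that ARH(1) fits badly. At the tested visits, ARH(1) alone was neutral or conservative under every covariance tried. The primary CMH analysis is untouched, and the rank-based ANCOVA sensitivity analysis does not use this covariance model. All of this stands and limits the severity. It does not remove the redundant term.

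**Conclusion.** The model as written in SAP 6.4.2 is over-parameterised by exactly one term. That is algebra and needs no assumption about the data. The consequence is conditional: the redundant term can trigger the ARH(1) fallback but need not.

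If ARH(1) is reached without a random effect, the sizes in the table apply only under the assumed 0.4 + 0.6·g^weeks covariance. They shrink with independent error and vanish under compound symmetry. The documents give no covariance, so no single figure can be claimed for this trial.

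Two further inferences are not supported. One is that Week 12 is safe: on the assumed covariance this holds for ESSDAI but not for ESSPRI, whose extra Week 2 visit makes the spacing more uneven. The other is that the single baseline slope is an error: a baseline-by-visit term is an optional refinement.

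Severity is minor: secondary endpoints of a proof-of-concept study, correctable by wording.

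**What to change.** 1. Delete the random subject effect from SAP 6.4.2, and state that within-subject correlation is modelled only through the unstructured matrix of repeated measures. Rank is then full: 15 of 15 and 21 of 21.
2. State that the fallback carries no random subject effect.
3. If the unstructured fit fails, use a named structure with visit-specific variances and correlation that depends on the actual weeks between visits.
4. Apply one structure across all 20 imputed data sets of an analysis: if any needs the fallback, all use it.

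Two substitutes for step 3 would not help. Heterogeneous Toeplitz also counts visits rather than weeks; on the covariance of Step 3 it overstates Week 24 variance by 6.4–7.2% (ESSDAI) and 16–18% (ESSPRI). Standard spatial power forces one variance on all visits.

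The correlation should also be allowed to level off, for example a + (1 − a)·g^weeks inside the repeated-measures matrix. A bare g^weeks with visit-specific variances understates Week 24 variance under compound symmetry (correlation 0.3–0.7) by 2–6% (ESSDAI) and 2–11% (ESSPRI). The levelling form contains both assumed covariances.

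The cost is a few sentences before the SAP is finalised for the Week 24 analysis, plus programming of a fallback that may never be used. Design, data collection and sample size do not change.

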6.5. Exploratory Efficacy Endpoints

CCI

[REDACTED]

[REDACTED]

[REDACTED]

[REDACTED]

[REDACTED]

CCI

CCI

CCI [REDACTED]

[REDACTED]

[REDACTED]

[REDACTED]

[REDACTED]

[REDACTED]

[REDACTED]

[REDACTED]

[REDACTED]

[REDACTED]

6.5.2. Analysis Methods for Exploratory Efficacy Endpoints

CCI [REDACTED]

[REDACTED]

[REDACTED]

CCI

The page contains two large black rectangular redaction boxes. The first box covers the text starting with 'CCI'. The second box covers the text starting with '6.6. Changes From Protocol-Specified Efficacy Analyses'.

6.6. Changes From Protocol-Specified Efficacy Analyses

The treatment policy, hypothetical and composite estimands have been added to the analyses of the primary and secondary endpoints.

7. SAFETY ANALYSES

The safety analyses will be performed for the placebo-controlled treatment period up to Week 24, and for the entire study duration. Analyses for these periods will be presented by the treatment groups specified in Section 3.

For the analyses of adverse events (AEs) that include data after Week 24 the exposure-adjusted analyses will be presented.

For the AEs, laboratory results and concomitant medication data, the collection/start date will be used to determine which reporting period the record belongs to. For other parameters collected on CRFs, the nominal visits will be used.

7.1. Adverse Events and Deaths

7.1.1. Adverse Event Dictionary

Clinical and laboratory AEs will be coded using the current version of MedDRA. System organ class (SOC), high-level group term (HLGT), high-level term (HLT), preferred term (PT), and lower-level term (LLT) will be provided in the AE dataset.

7.1.2. Adverse Event Severity

Adverse events are graded by the investigator as Grade 1, 2, 3, 4, or 5 according to toxicity criteria specified in the protocol (CTCAE 4.03). The severity grade of events for which the investigator did not record severity will be categorized as “missing” for tabular summaries and data listings. The missing category will be listed last in summary presentation.

7.1.3. Relationship of Adverse Events to Study Drug

Related AEs are those for which the investigator selected “Related” on the AE CRF to the question of “Related to lanraplenib/placebo”, “Related to filgotinib/placebo” or “Related to tirabrutinib/placebo”. If AE is reported as “Related” to any of 3 study drugs then the AE is considered “Related to study treatment”. Relatedness will always default to the investigator’s choice, not that of the medical monitor. Events for which the investigator did not record relationship to study drug will be considered related to study drug for summary purposes. However, by-subject data listings will show the relationship as missing.

7.1.4. Serious Adverse Events

Serious adverse events (SAEs) will be identified and captured as SAEs if the AEs met the definitions of SAEs that were specified in the study protocol. SAEs captured and stored in the clinical database will be reconciled with the SAE database from the Gilead Pharmacovigilance & Epidemiology Department before data finalization.

7.1.5. Treatment-Emergent Adverse Events

7.1.5.1. Definition of Treatment-Emergent Adverse Events

Treatment-emergent adverse events (TEAEs) of the entire study duration are defined as 1 or both of the following:

- Any AEs with an onset date on or after any study drug start date and no later than 30 days after permanent discontinuation of any study drug
- Any AEs leading to premature discontinuation of study drug.

TEAEs up to Week 24 are defined as 1 or both of the following:

- Any AEs with an onset date on or after Day 1 and no later than the day before the Week 24 treatment start date.
- For subjects who discontinued treatment prior to Week 24 visit, any AEs with an onset date no later than 30 days after permanent discontinuation of study drug

TEAEs of active treatment are defined similarly as the definition of the entire study duration, except that active study drug instead of any study drug will be used:

- Any AEs with an onset date on or after the first dose of active study drug and no later than 30 days after permanent discontinuation of active study drug.

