7.2.2. Assessment of Severity

The severity of AEs will be graded using the modified Common Terminology Criteria for Adverse Events (CTCAE), version 4.03. For each episode, the highest grade attained should be reported.

If a CTCAE criterion does not exist, the investigator should use the grade or adjectives: Grade 1 (mild), Grade 2 (moderate), Grade 3 (severe), Grade 4 (life-threatening) or Grade 5 (fatal) to describe the maximum intensity of the adverse event.

For purposes of consistency with the CTCAE, these intensity grades are defined in [Table 7-1](#) and [Appendix 4](#).

Table 7-1. Grading of Adverse Event Severity

Grade	Adjective	Description
Grade 1	Mild	Asymptomatic or mild symptoms; clinical or diagnostic observations only; intervention not indicated
Grade 2	Moderate	Local or noninvasive intervention indicated; limiting age-appropriate instrumental ADL*
Grade 3	Severe	Severe or medically significant but not immediately life-threatening; hospitalization or prolongation of hospitalization indicated; disabling; limiting self-care ADL**
Grade 4	Life-threatening	Urgent intervention indicated
Grade 5	Death	Death related AE

* Activities of Daily Living (ADL) Instrumental ADL refer to opening preparing meals, shopping for groceries or clothes, using the telephone, managing money, etc.

** Self-care ADL refer to bathing, dressing and undressing, feeding self, using the toilet, taking medications, and not bedridden.

7.3. Investigator Requirements and Instructions for Reporting Adverse Events and Serious Adverse Events to Gilead

Requirements for Collection Prior to Study Drug Initiation:

After informed consent, but prior to initiation of study medication, the following types of events should be reported on the case report form (CRF/eCRF): all SAEs and adverse events related to protocol-mandated procedures.

Adverse Events

Following initiation of study medication, collect all AEs, regardless of cause or relationship, until 30-days after last administration of study IMP must be reported to the CRF/eCRF database as instructed.

All AEs should be followed up until resolution or until the adverse event is stable, if possible. Gilead Sciences may request that certain AEs be followed beyond the protocol defined follow up period.

Serious Adverse Events

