3.2. Subject Grouping

For the analysis of placebo-controlled period (up to week 24), subjects will be presented by four treatment groups:

- Filgotinib 200 mg
- Lanraplenib 30 mg
- Tirabrutinib 40 mg
- Placebo

For the analyses of the entire study period, subjects will be grouped into seven treatment groups as specified in Table 1. For the analyses based on the FAS Analysis Set, subjects will be grouped according to the treatment to which they were randomized at Study Day 1 and Week 24. For the analyses based on the Safety Analysis Set, subjects will be grouped according to the actual treatment that they received. The actual treatment received will differ from the randomized treatment only when their actual treatment differs from randomized treatment for the entire treatment duration.

Table 1. Treatment Groups for the Entire Study Summaries

Filgotinib 200 mg	Filgotinib 200 mg from Study Day 1
Lanraplenib 30 mg	Lanraplenib 30 mg from Study Day 1
Tirabrutinib 40 mg	Tirabrutinib 40 mg from Study Day 1
Placebo/Filgotinib 200 mg	Placebo up to Week 24 and Filgotinib 200 mg after Week 24 first dose
Placebo/Lanraplenib 30 mg	Placebo up to Week 24 and Lanraplenib 30 mg after Week 24 first dose
Placebo/Tirabrutinib 40 mg	Placebo up to Week 24 and Tirabrutinib 40 mg after Week 24 first dose
Placebo	Placebo group with study drug withdrawn prior to or at Week 24 (not received drug assigned at Week 24)

For the PK Analysis Set, subjects will be grouped according to the actual treatment they received.

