Completion of the study up to Week 12 will be based on the presence of the corresponding visit in EDC or presence of Early Termination visit which is after Week 8 visit. Completion of treatment up to Week 12 is considered when the [date of last dose – date of first dose + 1] \geq 82 days (target date for Week 12 visit minus protocol allowed visit window). Similar algorithm is applied to Week 24 completion. Subjects are considered to complete 24 weeks of treatment if the start date of Week 24 treatment is provided or the [last dose date – first dose date + 1] \geq 166. Subjects who complete Week 24 visit/treatment but did not continue beyond Week 24 are reported as “Discontinued at Week 24”.

The by-subject listing of disposition will be provided by subject identification (ID) number in ascending order to support the above summary tables.

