7.2.2.1. Treatment-Emergent Laboratory Abnormalities

Treatment-emergent laboratory abnormalities for the entire study period and in subjects discontinued treatment prematurely are defined as values that increase at least 1 toxicity grade from baseline at any postbaseline time point, up to and including the date of last dose of study drug plus 30 days for subjects who permanently discontinued study drug, or the last available date in the database snapshot for subjects who were still on treatment at the time of an interim analysis. If the relevant baseline laboratory value is missing, any abnormality of at least Grade 1 observed within the time frame specified above will be considered treatment emergent.

For the analyses of active treatment period, the baseline is the day of the first dose of active study drug administration.

For the analyses of placebo-controlled period, the laboratory abnormality occurring after Week 24 visit and no later than 30 days after the last dose of study drug is included only if subject does not continue treatment after Week 24.

The listing of all laboratory abnormalities will be provided.

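### The SAP's definition of TEAEs up to Week 24 has no start bound for early discontinuers and no clear end for subjects who never start Week 24 treatment

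*SAP*

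**What the plan says.** SAP 7.1.5.1 counts an event as a TEAE up to Week 24 if it meets either or both of two alternatives:

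- The first alternative reads "Any AEs with an onset date on or after Day 1 and no later than the day before the Week 24 treatment start date".
- The second alternative, meant for early discontinuers, reads "For subjects who discontinued treatment prior to Week 24 visit, any AEs with an onset date no later than 30 days after permanent discontinuation".

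The SAP also plans for subjects who reach Week 24 and go no further. SAP 4.1 gives them their own disposition label: "Subjects who complete Week 24 visit/treatment but did not continue beyond Week 24 are reported as" having discontinued at Week 24. Table 1 in SAP 3.2 has a placebo row that includes subjects withdrawn at Week 24 who never took the drug assigned there.

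For laboratory data in the same period, SAP 7.2.2.1 says that an abnormality seen later than that visit but "no later than 30 days after the last dose of study drug is included only if subject does not continue treatment after Week 24".

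Protocol 7.3 has sites record, between consent and first dose, "all SAEs and adverse events related to protocol-mandated procedures". Such events are therefore in the adverse event data before any drug is taken.

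**The concern.** The first alternative depends on a Week 24 treatment start date. A subject who does not start Week 24 treatment has no such date. The second alternative is limited to subjects who stopped before the Week 24 visit. A subject who completes Week 24 and then stops is not clearly covered by either, so the text does not say where that subject's window closes.

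The second alternative also has an upper limit but no lower one. A pre-dose serious or procedure-related event in a subject who later stops early meets it as written. The same event in a subject who continues does not meet the first alternative.

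In both cases, classification depends on discontinuation status, which may differ between arms. The tables affected are the main ones for safety. Of the AE summaries in SAP 7.1.6, those for the placebo-controlled period compare each drug with the whole randomised placebo arm. The entire-study grouping splits placebo into four rows.

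**Working it through.** **Inputs.** Week 24 target day 169 (SAP Table 2); visit window of 3 days either side (SAP Appendix 1); 35 subjects per arm (Protocol 3.2); the two alternatives in SAP 7.1.5.1.

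**The plan's own figure.** SAP 4.1 treats 24 weeks of treatment as complete at 166 days or more. This reproduces: 169 − 3 = 166 (and for Week 12, 85 − 3 = 82). A subject whose last dose is on Day 166, 167 or 168 is therefore a Week 24 completer for disposition, even though that dose precedes a Day 169 visit. Disposition and the TEAE rule draw the line on different bases.

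**Applying the rule.** Take first dose on Day 1 and the Week 24 visit on Day 169. A missing Week 24 start date can be read in two ways: under A the first alternative fails; under B it has no upper limit. Subjects who stop at Week 24 are taken here as outside the second alternative. The last column is the rule proposed under the fix.

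| Subject | Onset | A | B | Proposed |
|---|---|---|---|---|
| Continues past Week 24 | Day 100 | in | in | in |
| Continues past Week 24 | Day 169 | out | out | out |
| Stops at Week 24, last dose Day 168 | Day 100 | out | in | in |
| Stops at Week 24, last dose Day 168 | Day 180 | out | in | in |
| Stops at Week 24, last dose Day 168 | Day 198 | out | in | in |
| Stops at Week 24, last dose Day 168 | Day 230 | out | in | out |
| Stops on Day 60 | Day −10 | in | in | out |
| Stops on Day 60 | Day 50 | in | in | in |
| Stops on Day 60 | Day 85 | in | in | in |
| Stops on Day 60 | Day 120 | out | in | out |

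For the Week 24 stopper the 30-day limit falls at 168 + 30 = Day 198; Day 230 is 230 − 168 = 62 days after the last dose. For the Day 60 stopper the limit is 60 + 30 = Day 90; Day 120 is 60 days after stopping. The Day −10 event counts under both readings, because the second alternative admits it whatever is done with the missing date. Subjects who continue are classified as intended.

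**A third reading.** If a last dose on Day 168 counts as stopping before the Day 169 visit, the second alternative applies. With a missing date failing the first alternative, the Day 100, 180 and 198 events are in and Day 230 is out, as under the proposed rule. The missing start bound then applies to these subjects too.

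**Size.** Each reclassified subject moves an arm's any-TEAE rate by at most 1/35 = 2.9 points. SAP 7.1.6 counts a subject once per summary, so the rate moves only if that subject has no other qualifying TEAE. Assuming 0 to 3 such subjects in an arm, the range is 0 to 3/35 = 8.6 points. The documents give no count.

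**The case against.** The strongest reply is that this is a drafting gap which other text closes.

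- *Week 24 stoppers.* Subjects hold their dose on the visit morning and take it in clinic (Protocol 6.9). SAP Table 2 pairs Day 169 with Day 1 of active treatment. Someone who declines the clinic dose will normally have taken the last dose before the visit, which is the third reading above. This is plausible, but the separate disposition category leaves it unsettled.
- *Loss of the whole record.* A reader might infer from reading A that a Week 24 stopper's entire 24-week AE record is lost. The documents do not support that. SAP 7 assigns each AE to a reporting period by its start date, so a Day 100 event belongs to the placebo-controlled period. What stays open is the tail after Week 24.
- *Events beyond 30 days.* Under reading B the window has no end, but Protocol 7.3 collects AEs only to 30 days after the last dose, while SAEs are reported throughout the study. Late additions would be mainly SAEs.
- *Pre-dose events.* Protocol 8.6 and 8.6.2 start the safety window at first dispensing or drug start, SAP 7.1.5.2 applies a first-dose bound to incomplete onset dates, and SAP 7.7 declares no deviation from the protocol. These show what was meant. They do not override the more specific Week 24 rule: the protocol sets no Week 24 cut. The SAP 7.7 statement is weak evidence too, because the Week 24 definition also omits the protocol's limb for AEs leading to discontinuation of study drug and does not list that as a change.
- *Size.* The figure of 2.9 points is a ceiling per subject, and only serious and procedure-related events can enter before dosing. Both limits stand.

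**Conclusion.** The definition is faulty as written, in two specific ways. Its second alternative has no lower bound, so pre-dose SAEs and procedure-related AEs of early discontinuers literally count as treatment-emergent. Its end is not clearly defined for subjects who complete Week 24 and do not start Week 24 treatment, although the laboratory rule for the same period does define it.

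A reader might go further and infer that the placebo-controlled safety table is wrong. That does not follow. No error in a table is shown: the result depends on how a missing date is programmed and on how many subjects stop at Week 24 or have a recorded pre-dose event, and the documents give neither. The realistic effect is confined to pre-dose events and the 30-day tail after Week 24. It is at most 2.9 points per reclassified subject, assuming 35 per arm and no other qualifying TEAE in that subject. The point is still worth settling before the Week 24 unblinding, because following the rule literally can misclassify events by discontinuation status.

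**What to change.** Replace the two alternatives in SAP 7.1.5.1 with one rule. A TEAE up to Week 24 has its onset on or after the first dose of study drug, and no later than:

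- (a) the day before Week 24 treatment starts, for subjects who start it; or
- (b) last dose plus 30 days, for all subjects who do not, whether they stop before or at Week 24.

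This matches the principle in SAP 7.2.2.1 and leaves subjects who continue unchanged. The cost is about two lines of SAP text. The dates needed are already collected, so no new data are required. SAP 1 says the plan is finalised before the Week 24 analysis, which is the time to make the change.
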